However, a large multicenter RCT (PLATO)[9] showed a statistically significant decrease in composite CV outcomes with the newer ticagrelor compared to clopidogrel. This has prompted both European[6] and Canadian[8] guideline writers to endorse ticagrelor / aspirin as the DAPT of choice. However residual uncertainties regarding the choice of DAPT are highlighted by the PLATO subgroup analysis[9] that showed an increased risk with ticagrelor in North America (NA) patients. This led to delayed FDA approval, dissenting FDA reviews[10] and an unwillingness of US guidelines [7] to recommend the ticagrelor DAPT regime over others.

[figure not shown]
2) The specific need for another DAPT RCT Do we really need a replication study after an 18,000 patient RCT showed a statistically significant decrease in composite CV outcomes? Unfortunately, as I have demonstrated in two peer review publications, the answer is an unequivocal yes[11, 12]. While the integrity of the PLATO data has been questioned by some [13-15], the main area of uncertainty, at least from a NA perspective, hinges on the small number of NA patients randomized in this trial and their increased risk with ticagrelor (n=1814, HR 1.25; 95% CI 0.93 - 1.67). The risk in NA patients was statistically significantly different from the benefit seen in the other subgroups (p=0.04) and the crux of the debate is then whether to believe the subgroup analysis or the combined study results (n=18624, HR, 0.84; 95% CI 0.77 to 0.92). The complete study provides maximal information but perhaps at a cost of being less representative of what to expect in NA practice. Conventional statistical paradigms would say that given the pre-specified nature of the geographic subgroup analysis and given the statistically significant interaction observed, one should concentrate on the subgroup results and not the combined results.

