more towards the study mean [11] but by acknowledging between group variations, the uncertainty around the overall population mean result increases. Thus simply changing the statistical model to the more reasonable hierarchical (random effects model) while using the same PLATO data results in a similar combined point estimate of 0.86 but with 95% CI 0.49 to 1.60. It is worth taking a moment to fully understand what these intervals from the 2 different models are actually providing and recognizing the important differences. For the original NEJM analysis, the point estimate and confidence interval have assumed no between region variation and the result thus provides the best estimate of a common treatment effect, and the confidence interval depicts the uncertainty around this estimate. For the hierarchical model, the point estimate and confidence interval have acknowledged the between region variation and the result provides an estimate of the average treatment effect, and the confidence interval depicts the uncertainty around this estimate. Ignoring heterogeneity, such as possible regional variation, may lead to a false sense of certainty with an overly precise summary result (that is, the confidence interval is too narrow) and may incorrectly imply that a common treatment effect exists when actually there are meaningful differences in treatment effectiveness across regions. Finally, as has been cogently argued by others[16] with hierarchical models it appropriate to consider not only the average result but also the prediction interval which gives the range of possible values of the next study. The prediction interval for the next ticagrelor / clopidogrel study is very wide (0.86, 95%CI 0.24 – 3.34) providing additional justification for this proposal.

The use of Bayesian hierarchical modeling also allows the formulation of probability statements.

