The Figure (white area represents clinical equivalence (+/- 15%), red & green areas are ticagrelor & clopidogrel superiority), plots the average hierarchical treatment interval as a probability density function, providing further justification for this proposal as it shows that the probability of clopidogrel non-inferiority (measured as white & green area under the curve) is 52% [11, 12]. Regardless of which statistical model one believes, the DAPT evidence base in favor of ticagrelor is obviously not robust when a simple change in the analytical model leads to extreme variability in conclusions. This project will resolve these uncertainties and address the crucial clinical question of which DAPT regime is best after an ACS? The financial stakes are also high with a potential increase by switching to ticagrelor in Quebec and Canadian drug costs of \$25 and \$100 million annually respectively with at present great uncertainty about any clinical benefits. This proposal will double the currently available evidence with a novel research design using inexpensive, electronic data and will provide a feasible answer to this important clinical question. Our approach using a valid, inclusive, generalizable study design will enable an accurate population assessment of drug side effects and long term patient compliance which are notoriously under reported in conventional industry sponsored trials[17].

Methods t

Regulatory agencies evaluate and approve drugs based on individually clinical randomized parallel two-arm trial (RCT) evidence due to their superior validity compared to non-experimental designs. Given that standard RCTs require major financial resources, the majority of large scale trials are industry sponsored

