Remember due to the between region variability this result (green curve) is not as definitive as implied in the original PLATO result as reported in the NEJM[9]. Next suppose that we are able only to recruit only 1500 (blue curve), not the expected 4000, patients but that the results are concordant with the overall PLATO results (green curve). The combined results will provide definitive results for the superiority of ticagrelor over clopidogrel with almost 100% probability as virtually all the area under the red curve is to the left of 0 line. In this circumstance, there is at least 80% probability that this superiority is clinically significant (defined as > 15% improvement, area under the red curve to the left of a vertical line at -0.15). Conversely suppose we also use the “skeptical” prior of PLATO’s NA subgroup and that our data again concurs, a scenario shown graphically in the Figure (right). In this case, the contribution of our data removes all uncertainty about DAPT in NA patients and we become virtually certain that clopidogrel is superior to ticagrelor (99% of the area under the red curve to the right of 0). It must be emphasized that these definitive conclusions are available using < 50% of our projected data and hence should allow definitive conclusions for all other combinations of prior and new data.

Study timeline

We project that patient recruitment will be 18-20 months. The primary outcome for this project will be safety and effectiveness outcomes at 12 month follow-up. The securing of outcome data from provincial databases

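### The 15% criterion for clinically significant superiority is read at -0.15 on an unnamed scale, and the stated probability of at least 80% is not reproduced on either plausible scale

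*Protocol*

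**What the plan says.** Anticipated results and conclusions works through a scenario in which only 1,500 patients are recruited and their results agree with overall PLATO. Superiority of ticagrelor is judged near certain because "virtually all the area under the red curve is to the left of 0 line". The protocol then says "there is at least 80% probability that this superiority is clinically significant", which is "defined as > 15% improvement, area under the red curve to the left of a vertical line at -0.15". The text names no axis scale, and the figure is not available here.

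The same 15% limit appears in Knowledge to date, item 2, where the "white area represents clinical equivalence (+/- 15%), red & green areas are ticagrelor & clopidogrel superiority". From that figure the protocol reports that "the probability of clopidogrel non-inferiority (measured as white & green area under the curve) is 52" per cent. No scale is given there either.

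The PLATO results offered as prior information are hazard ratios. The conventional analysis is "n=18624, HR, 0.84; 95% CI 0.77 to 0.92", and the hierarchical re-analysis has a "similar combined point estimate of 0.86 but with 95% CI 0.49 to 1.60".

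**The concern.** One criterion is given in two forms, a percentage improvement and a position on an axis, and the two agree on only one of the scales the axis could have. The text then attaches a probability to that criterion.

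This matters because the primary analysis is Bayesian and its stated advantage is direct probability statements. The 15% line is also the protocol's only definition of clinically significant superiority. The planning effect (10% against 12%, ratio 0.833) and the PLATO estimates (0.84 and 0.86) all lie almost on that line, so a small move of the cut-off changes the probability noticeably. If the cut-off stays ambiguous, it could be chosen after outcomes are known. A reader of the scenario may also expect far more certainty about a clinically important benefit than the stated inputs give.

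**Working it through.** **Step 1. Which scale?** The null is 0, so the axis is not the raw hazard ratio. It is not an absolute risk difference, because -0.15 would exceed the 12% control risk. Two readings remain:
- Log HR: exp(-0.15) = 0.861, a 13.9% improvement; a 15% improvement is ln 0.85 = -0.1625.
- HR minus 1: 0.85 - 1 = -0.15, so the line is exactly right.

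**Step 2. Inputs.**
- Conventional PLATO prior: mean ln 0.84 = -0.1744; SD = (ln 0.92 - ln 0.77)/3.92 = 0.0454.
- Hierarchical PLATO prior: mean ln 0.86 = -0.1508; SD = (ln 1.60 - ln 0.49)/3.92 = 0.3019.
- New data: 1,500 patients, 750 per arm. The 12% and 10% risks in Sample size calculations give 90 and 75 events, so SE = sqrt(1/90 + 1/75) = 0.1563. Concordant is taken as HR 0.84.

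The update is inverse-variance weighting of two normal distributions on the log scale. The probability is Phi((line - posterior mean)/posterior SD).

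**Step 3. Check the method on the protocol's other scenario.** The North American prior is HR 1.25 (0.93 to 1.67), SD = (ln 1.67 - ln 0.93)/3.92 = 0.1493. With 1,500 patients also at HR 1.25, the posterior SD is 1/sqrt(1/0.1493² + 1/0.1563²) = 0.1080. The probability above 0 is Phi(0.2231/0.1080) = 98.1%; the protocol says 99%. The method is a fair check.

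**Step 4. Try to reproduce the 80%.**

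| Prior | Posterior mean | Posterior SD | Below 0 | Below -0.15 | HR < 0.85 (below -0.1625) |
|---|---|---|---|---|---|
| Conventional | -0.1744 | 0.0436 | 100.0% | 71.2% | 60.7% |
| Hierarchical | -0.1694 | 0.1388 | 88.9% | 55.5% | 52.0% |

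The last column is also the answer if the axis is HR minus 1.

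**Step 5. Variants.**
- Data at 10/12 with the log-risk-ratio SE, sqrt(0.88/90 + 0.90/75) = 0.1476: hierarchical 57.8% and 54.1%, conventional 71.8% and 61.4% (line at -0.15, then HR 0.85).
- The same, reading 1,500 as per arm: 61.5% and 56.6% hierarchical, 73.1% and 62.4% conventional.
- Data at HR 0.86 instead, 1,500 patients and the Step 2 SE: lower, 50.2% and 46.6% hierarchical, 69.7% and 59.1% conventional.
- All 4,000 patients: at most 73.9% at -0.15.

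Excluding the HR 0.86 variant and the 4,000-patient case, the ranges over both lines are about 52 to 62% (hierarchical) and 61 to 73% (conventional).

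**Step 6. What would 80% need?** With a posterior mean at HR 0.84, 80% below -0.15 needs an SD of (0.1744 - 0.15)/0.8416 = 0.029. The smallest SD obtained with 1,500 patients is 0.043.

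**Step 7. How much is the line?** With the conventional prior, moving the line costs 71.2 - 60.7 = 10.5 points, but the stated 80% is already 8.8 points above the value at the unmoved line. With the hierarchical prior, the shift is 55.5 - 52.0 = 3.5 points and the gap at the unmoved line is 24.5 points.

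**The case against.** The strongest reply is that the scale is inferred from a figure nobody here can see. An axis of relative change is a sensible choice, and on it the line is exactly where it should be. This stands: the text does not prove a misplaced line.

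A reader might take the 52% in Knowledge to date as proof that two different cut-offs were used. With the hierarchical result centred at ln 0.86, a limit of HR 0.85 gives 51.5% and -0.15 gives 49.9%. The documents do not support that inference. The interval 0.49 to 1.60 is not symmetric about 0.86 on the log scale; centring on its log midpoint gives 55.4% and 53.7%. Moreover, HR 0.85 is also what an HR-minus-1 axis with a line at -0.15 would give, so the match cannot tell the two readings apart.

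It can also be said that the passage illustrates a hypothetical result and that Statistical analysis fixes no 15% decision rule. That is right, and it limits the consequence. It does not remove the point, because Statistical analysis sends the reader to this section for a fuller description and no other definition of clinical significance is given.

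Lastly, the 10-point figure uses the conventional prior, although the text says the plotted prior is less definitive than the published result. That is fair. Yet the hierarchical prior, which fits that description, moves the probability further from 80% and does not give near certainty below 0 either (88.9%).

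**Conclusion.** The point holds in two parts. First, the criterion is ambiguous: on a log-HR axis the line marks a 13.9% improvement and overstates the probability by about 4 to 10 points, depending on the prior; on an HR-minus-1 axis it is correct. Log HR is the more natural reading because the priors are hazard ratios and the null is 0, but it remains an inference.

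Second, and on either scale, the probability of at least 80% does not follow from the stated priors and 1,500 concordant patients.

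Two stronger readings are not supported. One is that the protocol contains a proven arithmetic error in the line. The other is that the line explains why the 80% is too high; Step 7 shows that it accounts for only part of the shortfall. The plotted curves may rest on inputs the text does not give, so the figure is properly called not reproduced.

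The numbers assume normality on the log scale, the planning event rates, equal arms and no clustering. Allowing for clustering would widen the posterior and, with the centre at HR 0.84, lower these probabilities further.

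**What to change.** - Name the scale of the axis in Anticipated results and conclusions.
- State the criterion as HR < 0.85, equivalently log HR < ln 0.85 = -0.163, and compute it as the share of MCMC draws that meet it. The answer then does not depend on how the curve is drawn.
- Put the 15% equivalence zone in Knowledge to date on the same hazard-ratio scale. If it means HR 0.85 to 1.15, its log limits are -0.163 and +0.140.
- Say which PLATO prior the green curve represents, then recompute and restate the probability of at least 80%.

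The cost is a few sentences, one threshold in the analysis code and one rerun of the illustration. The price is that the illustrated probability of a clinically significant benefit becomes clearly less favourable.

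### The probabilities given for the enthusiastic-prior scenario at 1,500 patients do not follow from the protocol's own inputs, and two concordant scenarios cannot show that every other combination will be definitive

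*Protocol*

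**What the plan says.** Under Anticipated results and conclusions, the protocol takes an enthusiastic prior built from all PLATO data. It says that "due to the between region variability this result (green curve) is not as definitive as implied in the original PLATO result", so the curve is the one widened for regional variation. That model is quantified under Knowledge to date, item 2, where it "results in a similar combined point estimate of 0.86 but with 95% CI 0.49 to 1.60". The conventional result appears in the same item as "combined study results (n=18624, HR, 0.84; 95% CI 0.77 to 0.92".

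The section then adds 1,500 patients, instead of the expected 4,000, whose results agree with PLATO. It states that the combination provides "definitive results for the superiority of ticagrelor over clopidogrel with almost 100% probability" and that "there is at least 80% probability that this superiority is clinically significant", the latter read off as the area beyond -0.15. A second scenario pairs the North American (NA) subgroup prior with concordant data and reports 99% in favour of clopidogrel. Because these scenarios use under half the projected data, the section concludes that the full study "hence should allow definitive conclusions for all other combinations of prior and new data".

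**The concern.** Adding 1,500 patients to a prior as wide as 0.49 to 1.60 should leave a posterior that still spans 1. A posterior centred close to the 15% cut also cannot put 80% of its mass beyond that cut unless it is very narrow. Both stated probabilities therefore looked too high.

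The generalisation looked unsafe for a separate reason. Both scenarios have new data that agree with the prior, which is when a posterior sharpens most in one direction. They say nothing about disagreement. That case matters because the section on sample size names the NA patients as the prior for the main Bayesian analysis, so a PLATO-like result in this trial would be discordant with it.

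At stake is an assurance to funders and the ethics board about how conclusive the primary Bayesian analysis will be if recruitment falls short.

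**Working it through.** **Inputs from the protocol**
- Hierarchical PLATO prior: HR 0.86 (0.49 to 1.60). Log mean ln 0.86 = -0.151; SD = (ln 1.60 - ln 0.49)/3.92 = 0.302.
- Published PLATO: HR 0.84 (0.77 to 0.92). Log mean -0.174; SD 0.045.
- NA subgroup: HR 1.25 (0.93 to 1.67). Log mean 0.223; SD 0.149.
- Event rates 12% vs 10%, from Sample size calculations.

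**Assumptions:** equal arms, normal curves on the log scale, no clustering unless stated.

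**Check of the prior.** The protocol states that the "probability of clopidogrel non-inferiority (measured as white & green area under the curve) is 52" per cent. A normal curve with mean -0.151 and SD 0.302 gives P(HR > 0.85) = 0.515, so the prior is read as the protocol intends.

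**Data.** 750 per arm at 12% and 10% give 90 and 75 events. SE = √(1/90 + 1/75) = 0.156. The rates imply HR = ln 0.90/ln 0.88 = 0.824, log -0.193.

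**Update.** Posterior mean = (m₀/s₀² + d/SE²)/(1/s₀² + 1/SE²); posterior SD = (1/s₀² + 1/SE²)^(-1/2). With the hierarchical prior the weights are 1/0.302² ≈ 10.97 and 1/0.156² ≈ 40.9. For data at 0.824 the mean is (10.97 × -0.151 + 40.9 × -0.193)/51.9 = -0.184, SD 0.139. P(HR < 1) = Φ(0.184/0.139) = 0.91.

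| Prior, 1,500 concordant patients | Data HR | P(HR < 1) | P(log HR < -0.15) | P(HR < 0.85) |
|---|---|---|---|---|
| Hierarchical | 0.824 | 0.91 | 0.60 | 0.56 |
| Hierarchical | 0.84 | 0.89 | 0.56 | 0.52 |
| Hierarchical | 0.86 | 0.86 | 0.50 | 0.47 |
| Published PLATO | 0.84 | 1.00 | 0.71 | 0.61 |
| Published PLATO | 0.86 | 1.00 | 0.70 | 0.59 |
| **Protocol states** | | **almost 1** | **at least 0.80** | |

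On the odds-ratio scale the hierarchical row peaks at 0.91 and 0.61, and the published-PLATO row reaches 0.73 beyond -0.15. Reading 1,500 as per arm, with the hierarchical prior, gives 0.93 to 0.965 and at most about 0.67.

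For 80% beyond -0.15 the posterior SD must be (-0.15 - mean)/0.842. That is 0.038 if the centre is 10/12 and 0.029 if it is 0.84, against 0.139 here.

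**Clustering.** The sample-size section moves from 3,000 patients to 4,000 or 4,800, which implies inflation of 1.33 or 1.6. Applied to the data variance, P(HR < 1) at 12% vs 10% falls from 0.91 to 0.88 or 0.86.

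**Sceptical scenario.** NA prior plus 1,500 patients at HR 1.25 gives P(HR > 1) = 0.981 to 0.985, close to the stated 99%.

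**Other combinations at 4,000 patients** (240 and 200 events, SE 0.0957, no clustering)

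| Prior | Data HR | P(HR < 1) | P(0.85 < HR < 1.15) | P(log HR within ±0.15) |
|---|---|---|---|---|
| NA | 0.84 | 0.77 | 0.89 | 0.87 |
| NA | 0.90 | 0.55 | 0.94 | 0.94 |
| Hierarchical | 0.90 | 0.885 | 0.72 | 0.67 |

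**The case against.** The strongest defence is that the protocol treats ±15% as clinical equivalence, an outcome in its own right. A reader might infer that discordant cases are all uninformative, and that does not hold: NA prior plus data at 0.90 puts 0.94 in the band, which is close to a definitive finding of equivalence. What remains is narrower. With the hierarchical prior and data at 0.90, neither superiority (0.885) nor equivalence (about 0.7) is settled, and one such case is enough to defeat a claim about all combinations.

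The figure is not shown, so the widths of its curves are inferred. The 52% check supports the width of the prior but says nothing about the new-data curve, which is derived here from the protocol's event rates. The axis scale is not named either. A reader might call the cut at -0.15 an error because ln 0.85 = -0.1625, but on a relative-difference axis -0.15 is exactly 15%. That criticism is therefore conditional.

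The sceptical illustration is essentially right, and the sentence on other combinations is hedged with should. The hedge softens the claim but does not supply the missing support.

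**Conclusion.** The point holds in this form. From the protocol's own inputs, the enthusiastic scenario gives about 0.86 to 0.91 for superiority and 0.47 to 0.61 for a gain above 15%, not almost 100% and at least 80%. The published PLATO interval, which the section itself regards as too definitive, supplies the first figure but not the second (0.59 to 0.73). The step from two concordant scenarios to all combinations is unsupported.

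The results rest on normal approximations, equal arms and independent patients. The shortfall persisted across the effect scales, data effects and sample splits tried, and allowing for clustering lowers the superiority figure further.

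Two stronger inferences are not supported. Nothing in the protocol makes 1,500 patients a target or stopping point; it calls 4,000 the expected number. Nor is this section the only argument for adequacy, since the sample-size section gives a power calculation and claims a safety margin from the prior. The section illustrates expected results and sets no decision threshold, so the error misstates how conclusive the design is without changing the planned analysis.

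**What to change.** Delete the sentence claiming definitive conclusions for all other combinations. Recompute the two enthusiastic-scenario probabilities from the stated hierarchical prior, with a variance that allows for clustering by period, and print them with their assumptions: arm split, event rates, data effect and clustering parameter. They should be expected to come out no higher than about 0.9 and 0.6. The unclustered values above should not be copied in as replacements.

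Add a short table of posterior probabilities of superiority, equivalence and inferiority for concordant and discordant prior/data pairs at 1,500 and 4,000 patients. State the scale of the axis; if it is log HR, note that a 15% reduction lies at ln 0.85 = -0.1625.

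The cost is one small calculation, some rewording and less favourable stated probabilities. Design, recruitment and the planned analysis are unaffected.

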Our proposed pragmatic, randomized – registry, cluster crossover randomized clinical trial is a novel design well suited to evaluating DAPT comparative effectiveness and addressing a pertinent patient orientated research question. The design can be seamlessly integrated into routine practice with minimal costs or ethical barriers, logistical feasibility, increased generalizability and enhanced capture of effectiveness and safety parameters. The proposed novel design and analysis of this trial will allow a timely answer to an important clinical question to be obtained in a very efficient manner at a small fraction ($<1/100$) of the cost of a standard RCT and a small fraction of the projected annual ticagrelor cost ($<1/1000$). While the main objective of this project is the evaluation of clinical effectiveness and safety outcomes, the structure of the project and the expertise of the team members will provide the data sources to permit later ancillary investigations into long term outcomes, quality of life, genomic and economic substudies. The project will also provide the first opportunity to look at long term comparative outcomes and will offer unique training opportunities.

Data analysis Amendment Oct 29 2019 While we obtain baseline patient information at the time of recruitment, follow-up data is obtained from the RAMQ provincial electronic records (patients sign consent at recruitment) as there are no follow-up direct patient visits with the research team. Historically we would apply to RAMQ and they would send us the follow-up data for consented patients. I was informed last week that this process has now been modified. Data will only be released to Centre d'accès aux données de recherche de l'Institut de la statistique du Québec (CADRISQ) and all analyses must be performed on their physical site. Therefore we must take our MUHC baseline data to CADRISQ, merge and then analyse the data at their site. Consequently I require an amendment to the protocol and a letter of authorization from the REB that I can submit to CADRISQ.

References

1. Antithrombotic Trialists C. Collaborative meta-analysis of randomised trials of antiplatelet therapy for prevention of death, myocardial infarction, and stroke in high risk patients. *Bmj.* 2002;324(7329):71-86. PubMed PMID: 11786451; PubMed Central PMCID: PMC64503.
